## 6.2. Study Period

### 6.2.1. Months 3, 9, 15, 21, 27, 33, 39, 45, 51, 57, 63, 69, 75, 81, 87, 93, 99, 105, 111, 117

Subjects will be contacted by telephone, contact is to be made  $\pm$  1 week of scheduled time:

- Assessment of ambulatory status (mPND);
- Ask subjects non-leading questions such as “How do you feel?” and document adverse events;
- Record concomitant medications;
- Ask about possibility of pregnancy;
- Mail 3 month supplies of investigational product following telephone contact;
- These telephone visits can be conducted in person at the clinic at the discretion of the sites.

---

#### **6.2.2. Months 6, 18, 30, 42, 54, 66, 78, 90, 102, 114**

Subjects will return to the clinic for the following assessments. Visits are to occur  $\pm$  2 weeks of the scheduled time:

- Collect blood/urine samples for laboratory assessments (section [7.3](#));
- Urine pregnancy test (for women of childbearing potential);
- Assessment of ambulatory status (mPND);
- Ask subjects non-leading questions such as “How do you feel?” and record adverse events;
- Record concomitant medications;
- Determine drug compliance and accountability;
- Dispense 3 month supply of investigational product.

#### **6.2.3. Months 12, 24, 36, 48, 60, 72, 84, 96, 108**

Subjects will return to the clinic for the following assessments. Visits are to occur  $\pm$  2 weeks of the scheduled time:

- Perform abbreviated physical exam and measure vital signs;
- Collect blood/urine samples for laboratory assessments (section [7.3](#));
- ECG;
- Urine pregnancy test (for women of childbearing potential);
- Assessment of ambulatory status (mPND);
- Perform NIS;
- Administer Norfolk QOL-DN;
- Determine Karnofsky Performance Scale Index;
- Ask subjects non-leading questions such as “How do you feel?” and record adverse events;
- Record concomitant medications;
- Determine drug compliance and accountability;

---

- Dispense 3 month supply of investigational product.

#### **6.2.4. End of Study Visit**

The end of study visit will occur upon subject withdrawal from the study or upon subject completion, which will be up to 10 years or until subject has access to tafamidis for TTR-FAP via prescription. Upon regulatory approval for the treatment of TTR-FAP in their respective country and access to prescription tafamidis, subjects may be withdrawn from the study. The decision to withdraw subjects in a country will be done in consultation between the investigator and the sponsor (see Section 6.3), subject withdrawal (for any reason), or program discontinuation by the Sponsor. The following activities will be completed:

- Complete physical examination, weight and vital signs, including assessment of the following body systems: general appearance, head and neck, eyes, ears, nose, throat, respiratory, genitourinary, endocrine, cardiovascular, abdomen, skin, musculoskeletal/musculoskeletal, neurological, immunologic/allergies, hematologic/lymphatic;
- ECG;
- Urine pregnancy test (for women of childbearing potential) and determination of pregnancy;
- Assessment of ambulatory status (mPND);
- Perform NIS;
- Administer Norfolk QOL-DN;
- Determine Karnofsky Performance Scale Index;
- Ask subjects non-leading questions such as “How do you feel?” and record adverse events;
- Electrocardiogram (unless performed within 6 months prior);
- Collect blood/urine samples for laboratory assessments (Section 7.3);
- Record concomitant medications;
- Determine drug compliance and accountability.

---

In the event a subject is unable to return to the study site for the end of study visit, telephone contact with the subject approximately 30 days after the last dose of medication to assess adverse events and concomitant medications and treatments is expected. If laboratory assessments are needed to follow-up unresolved adverse events, retrieval of assessments performed at an institution local to the subject is acceptable.

The outcome of adverse events with a date of onset during the study period should be reevaluated, and any new adverse events should be recorded. All serious adverse events, and those non-serious adverse events assessed by the investigator as possibly related to study drug should continue to be followed even after subject withdrawal from study. These adverse events should be followed until they resolve or until the investigator assesses them to be “chronic” or “stable”. Additional information on [ADVERSE EVENT REPORTING](#) can be found in Section 8.

### **6.3. Subject Withdrawal**

Subjects may withdraw from the study at any time at their own request, or they may be withdrawn at any time at the discretion of the investigator or sponsor for safety or behavioral reasons, or the inability of the subject to comply with the protocol required schedule of study visits or procedures at a given study site. In addition, the Sponsor may choose to discontinue this study, at which time all subjects will be withdrawn.

A subject may be withdrawn from the study for any of the following reasons:

- Withdrawal of consent;
- Adverse event;
- Protocol noncompliance;
- Subject lost to follow-up;
- Subject death.

Subjects who are prematurely withdrawn from the study will not be replaced. Subjects who discontinue from the study at any time following enrollment will have a final end of study visit performed, including all safety and efficacy assessments, at the time of discontinuation.

Subjects undergoing liver and or heart transplantation while participating in this study will no longer receive investigational product. However, subjects who do undergo a liver transplant will not be withdrawn from this study and will be asked to return to the clinical unit post-transplantation on an annual basis for NIS, Norfolk QOL-DN, and Karnofsky Performance Scale Index evaluations, safety assessments, and to assess subject ambulation. Further relevant information for the Investigator to consider for any subject undergoing liver transplantation is provided in [Appendix 4](#).

---

Upon regulatory approval of tafamidis for the treatment of TTR-FAP in their respective country, and access to prescription tafamidis, subjects may be withdrawn from the study. The decision to withdraw subjects in a country will be done in consultation between the investigator and the sponsor. Subjects will have all end of study procedures completed prior to study withdrawal. These subjects are considered completers.

If a subject does not return for a scheduled visit, every effort should be made to contact the subject. In any circumstance, every effort should be made to document subject outcome, if possible. The investigator should inquire about the reason for withdrawal, request the subject to return all unused investigational product(s), request the subject to return for a final visit, if applicable, and follow-up with the subject regarding any unresolved adverse events (AEs).

If the subject withdraws from the study, and also withdraws consent for disclosure of future information, no further evaluations should be performed, and no additional data should be collected. The sponsor may retain and continue to use any data collected before such withdrawal of consent.

## 7. ASSESSMENTS

Every effort should be made to ensure that the protocol required tests and procedures are completed as described. However it is anticipated that from time to time there may be circumstances, outside of the control of the investigator, that may make it unfeasible to perform the test. In these cases the investigator will take all steps necessary to ensure the safety and well being of the subject. When a protocol required test cannot be performed the investigator will document the reason for this and any corrective and preventive actions which he/she has taken to ensure that normal processes are adhered to as soon as possible. The study team will be informed of these incidents in a timely fashion.

### 7.1. Efficacy Assessments

The NIS, Norfolk QOL-DN, and Karnofsky Performance Scale Index evaluations will be performed on an annual basis when subjects return to the clinical unit for study visits (ie, every other 6-month visit).

For subjects who successfully completed Protocol Fx1A-201, the NIS, Norfolk QOL-DN, and Karnofsky scores from the end of study visit of Protocol Fx1A-201 will serve as Day 0 (Baseline) assessments for Protocol Fx1A-303/B3461023 if these procedures were performed within 30 days of Day 0. For subjects who successfully completed Protocol Fx-006, the Norfolk QOL-DN from the end of study visit from Protocol Fx-006 will serve as Day 0 (Baseline) if it was performed within 30 days of Day 0. In addition, the cranial nerve and upper limb components of the NIS will be performed on Day 0 and combined with the NIS-LL data from the end of study visit from Protocol Fx-006 and the Karnofsky Performance Scale Index will be assessed on Day 0 of Protocol Fx1A-303/B3461023.

Refer to [Appendix 1](#), [Appendix 2](#), and [Appendix 3](#), respectively, for the NIS, Norfolk QOL-PN, and Karnofsky Performance Scale Index efficacy evaluation forms.

---

The ambulatory status for each subject will be determined by the Investigator at each 6-month visit to the clinic as well as during telephone follow-up at 3-month intervals between clinic visits. The following scale, the modified polyneuropathy disability (mPND) score, will be used by clinical site staff to evaluate subject ambulation:

Score	Definition
0	Normal
I	Sensory disturbances in feet but able to walk without difficulty
II	Some difficulties walking but can walk without aid
IIIa	Able to walk with 1 cane or crutch
IIIb	Able to walk with 2 canes or crutches
IV	Not ambulatory; confined to wheelchair or bedridden

Source: ([Suhr, 1995](#); [Sharma, 2003](#)) 

## 7.2. Pregnancy

The end of study visit urine pregnancy test from Protocols Fx-006 and Fx1A-201 will be used as Day 0 (Baseline) for Protocol Fx1A-303/B3461023. If the pregnancy test is positive, the subject will be disallowed. Female subjects of child-bearing potential will be re-tested for pregnancy at every 6-month visit to the clinical unit and will be asked via telephone contact of possible pregnancy at 3-month intervals between clinic visits. A positive pregnancy test will lead to immediate discontinuation of investigational product and from the study. Subjects will also be instructed to notify the site should they become pregnant. In the event of a pregnancy, all investigational product must be discontinued immediately.

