## SCHEDULE OF ACTIVITIES

The Schedule of Activities table provides an overview of the protocol visits and procedures. Refer to Study Procedures (Section 6) and Assessments (Section 7) for detailed information on each procedure and assessment required for compliance with the protocol.

Procedure/Evaluation	End of study visit from Fx-006 or Fx1A-201 and/or Day 0 (Baseline)a	Open-label Investigational Product				End of study visit g
		Day 1	Telephone contact (every 3 months between clinic visits)	Clinic visits (every 6 months other than 12 month visits)	Clinic visits (every 12 months)	
Visit windows:		±1 week	±1 week	±2 weeks	±2 weeks	±2 weeks
Informed consent	X					
Inclusion/exclusion criteria	X					
Demographics	X					
Medical history	X					
Physical examination	X b				X b	X
Blood sample for laboratory testing c				X	X	X
Assessment of ambulatory status (mPND)			X	X	X	X
Urine test for pregnancy d	X			X	X	X
Pregnancy determination d			X			
Enrollment	X					
Dispense tafamidis e	X		X	X	X	
First dose of tafamidis		X				
Tafamidis compliance and accountability				X	X	X
NIS f	X				X	X
Norfolk QOL-DN f	X				X	X
Karnofsky Performance Scale Index f	X				X	X
ECG					X	X
Adverse events	X		X	X	X	X
Concomitant medication	X		X	X	X	X

Tafamidis meglumine  
Fx1A-303/B3461023  
Final Protocol Amendment 2, 05 June 2012

---

- a Relevant data from the end of study visits from Protocols Fx-006 and Fx1A-201 will be used for Day 0 (Baseline) if evaluations were performed within 30 days of Day 0.
- b The end of study physical examination (including weight and vital signs) from Protocols Fx-006 and Fx1A-201 will serve as Day 0 (Baseline) for Protocol Fx1A-303/B3461023 if these examinations were performed within 30 days of Day 0. An abbreviated physical examination (including weight and vital signs) will be conducted at every other 6-month visit. For blood pressure and pulse, measurements will be taken lying and standing.
- c Laboratory tests listed in Section [7.3](#).
- d Subjects with a positive result will be excluded or discontinued. Urine pregnancy test will be done at all clinic visits, subjects will be asked about potential pregnancies on phone contacts.

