### 6.1. Screening/Baseline Assessment

The end of study physical examination (including weight) and vital sign assessments from Protocols Fx-006 and Fx1A-201 will serve as Day 0 (Baseline) for Protocol Fx1A-303/B3461023 if these examinations were performed within 30 days of Day 0. If more than 30 days has passed between the final study visit of Protocols Fx-006 or Fx1A-201 and Day 0 (Baseline) for Protocol Fx1A-303/B3461023, all Day 0 study procedures will be performed (ie, no data from the final study visits from the previous studies will be utilized). For subjects who successfully completed Protocol Fx1A-201, the NIS, Norfolk QOL-DN, and Karnofsky scores from the end of study visit of Protocol Fx1A-201 will serve as Day 0 (Baseline) assessments for Protocol Fx1A-303/B3461023 if these procedures were performed within 30 days of Day 0. For subjects who successfully completed Protocol Fx-006, the Norfolk QOL-DN from the end of study visit from Protocol Fx-006 will serve as Day 0 (Baseline) if it was performed within 30 days of Day 0. In addition, the cranial nerve and upper limb components of the NIS will be performed on Day 0 and combined with the NIS-LL data from the end of study visit from Protocol Fx-006 and the Karnofsky Performance Scale Index will be assessed on Day 0 of Protocol Fx1A-303/B3461023.

Subjects will be required to sign an informed consent form before beginning participation in Protocol Fx1A-303/B3461023. The following procedures will be performed on Day 0:

- All inclusion and exclusion criteria will be reviewed to ensure eligibility for participation in this study;
- Demographics (date of birth, age, gender, and race) for all subjects will be collected;
- A complete medical history will be obtained;
- Urine test for pregnancy (women of child bearing potential only);
- Complete physical exam including weight and vital signs (if not conducted within 30 days of Day 0);
- NIS;

---

- For subjects who completed Fx1A-201, only if not performed within 30 days of Day 0;
- For subjects who completed Fx-006, the cranial nerve and upper limb components will be performed on Day 0 and combined with the NIS-LL from end of study visit from Fx-006, if performed within 30 days of Day 0. Otherwise all three components of NIS will be performed on Day 0.
- Norfolk QOL-DN, only if not performed within 30 days of Day 0.
- Karnofsky Performance Scale Index.
- For subjects completing Fx1A-201, only if not performed within 30 days of Day 0.

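### Protocol 7.2 takes the parent study's last urine pregnancy test as the Day 0 result with no time limit, which contradicts 6.1, the summary and the schedule

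*Protocol*

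**What the plan says.** Five places in the protocol bear on the Day 0 pregnancy result.

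- **Section 7.2 (Pregnancy)**, the section specific to this test: "The end of study visit urine pregnancy test from Protocols Fx-006 and Fx1A-201 will be used as Day 0 (Baseline". It names no time window and does not refer to one elsewhere. It then makes the result decisive for entry: "If the pregnancy test is positive, the subject will be disallowed".
- **Section 6.1 (Screening/Baseline Assessment), Day 0 list**: "Urine test for pregnancy (women of child bearing potential only". The item has no carry-over option. Other items in the list do, for example: "Complete physical exam including weight and vital signs (if not conducted within 30 days of Day 0".
- **Section 6.1, opening paragraph**: "If more than 30 days has passed between the final study visit of Protocols Fx-006 or Fx1A-201 and Day 0 (Baseline" of the new study, then "all Day 0 study procedures will be performed (ie, no data from the final study visits from the previous studies will be utilized".
- **Protocol summary, Study Design**: relevant parent-study assessments may serve as baseline if done within 30 days of Day 0. Beyond 30 days the same bar as in 6.1 applies.
- **Schedule of Activities**: the urine test is marked in a column that combines the parent study's final visit and/or Day 0. Footnote a allows relevant parent data for Day 0 if the evaluation was within 30 days. Footnote d says: "Urine pregnancy test will be done at all clinic visits".

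**The concern.** Pregnancy is exclusion criterion 3 in section 4.2, so the source and age of the Day 0 test bear directly on eligibility. A site that follows 7.2 as written can accept a parent result that 6.1, the summary and footnote a would not allow, and can then dispense drug at the same visit for a first dose the next day. Another site that follows 6.1 would test on Day 0. Each would be complying with one section and deviating from another.

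The test matters because the protocol itself reports developmental toxicity in rats and rabbits (section 1.2.3) and says that women who could become pregnant should take measures to avoid it. The issue is one of subject safety and consistent eligibility. It is not one of estimation or inference.

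**Working it through.** No arithmetic applies and the plan gives no figure to reproduce. The check sets the passages side by side for the two cases that the 30-day rule creates.

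| Place | Gap of 30 days or less | Gap of more than 30 days |
|---|---|---|
| 7.2 | Parent test is the Day 0 result | Parent test is the Day 0 result |
| 6.1, Day 0 list | Test on Day 0, no exemption | Test on Day 0, no exemption |
| 6.1, opening paragraph | Bar not triggered; the carry-over rules there do not mention the pregnancy test | Parent data barred; all Day 0 procedures done |
| Summary | Relevant parent assessments may serve | Parent data barred; all Day 0 procedures done |
| Schedule footnote a | Relevant parent data may serve | Outside the window in which parent data may serve |
| Schedule footnote d | Test at every clinic visit | Test at every clinic visit |

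**Beyond 30 days.** Read as written, 7.2 conflicts with both parts of 6.1, with the summary and with footnote a.

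**Within 30 days.** Section 7.2 and footnote a allow the parent result to stand. The 6.1 list calls for a test on Day 0. So does footnote d, provided Day 0 counts as a clinic visit; the summary has subjects report to the clinical unit that day. The combined column heading, with its and/or, does not settle the matter. Neither the summary nor footnote a says which parent data are relevant.

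**Is the missing exemption in 6.1 just loose drafting?** In the same list the physical examination, the NIS, the Norfolk QOL-DN and the Karnofsky index each carry a 30-day condition. For the NIS in Fx-006 completers it attaches to the lower-limb part, and for the Karnofsky it applies to Fx1A-201 completers only. The authors attached the condition item by item, and the pregnancy test has none.

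**Does the protocol rank its sections?** No. The introduction to the Schedule of Activities sends the reader to both Section 6 and Section 7 for what compliance requires, and gives no order of precedence.

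**What follows from the Day 0 result.** Sections 5.2.2, 6.1 and 6.2 give the sequence:

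1. Day 0: eligibility is reviewed and a 3-month supply is dispensed.
2. Day 1: first dose at home.
3. Month 3 (±1 week): a telephone question about pregnancy, then a further 3-month supply by mail.
4. Month 6 (±2 weeks): the next scheduled urine test.

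**The case against.** The strongest reply is that the general 30-day rule already governs. It stands in 6.1, in the summary and in footnote a, so a site would skip a Day 0 test after a long gap only by reading 7.2 alone. There is a parallel for reading the sections together. Section 7.1 and footnote f carry over the Fx-006 NIS-LL without a window in that sentence, and the 6.1 list supplies it. This stands as a reason not to treat the long-gap case as unregulated. It does not remove the contradiction. For the NIS-LL, 6.1 supplies a carry-over rule with a limit; for the pregnancy test it supplies no carry-over rule at all, so reading 7.2 together with 6.1 does not yield one rule. The disagreement within 30 days also remains even if the general rule prevails.

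A second reply is that other safeguards exist, and they do. Contraception is an entry condition for women (4.1, 4.3.1), the investigator confirms its use at each study visit, subjects must call at once if pregnancy is known or suspected, and all entry criteria are reviewed on Day 0. These reduce the risk but do not say which test counts.

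Third, the rule acts only at entry. Amendment 2 is dated June 2012 and section 1.2.4 already describes results from both parent studies, so much of the enrolment may be past. The documents do not say how many subjects remain to enter. This limits the practical reach of a change, but not the finding about the text.

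A reader might go further and infer that the protocol permits a parent test of any age and so allows months of undetected exposure in pregnancy. The documents do not support that. It requires 7.2 to be read without the 30-day bar stated elsewhere, it leaves out the safeguards above, and no gap between the parent visit and Day 0 is reported anywhere.

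**Conclusion.** The point holds as an internal contradiction in the current protocol. Section 7.2 disagrees with 6.1, the summary and footnote a when the gap exceeds 30 days. When the gap is 30 days or less, 7.2 and footnote a disagree with the 6.1 list and with footnote d.

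Its reach is limited to women of childbearing potential at entry. How many were affected, and by how long a gap, cannot be derived from the documents, so no frequency or duration of exposure is claimed. No sample size, estimate or analysis depends on it. It is still more than a missing detail, because the result bears on an exclusion criterion and drug is dispensed at the same visit.

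The conclusion assumes that no unseen site instruction sets an order of precedence between Sections 6 and 7. The reading of footnote d also assumes that Day 0 is a clinic visit; without that, the 6.1 list alone still conflicts with 7.2.

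**What to change.** The sponsor should reconcile 7.2 with 6.1, the protocol summary, the Schedule of Activities and footnotes a and d, so that a single rule states which urine test serves as the Day 0 result and how old it may be. The places that do not hold the rule should refer to the one that does. Which rule to adopt is a clinical decision for the sponsor, and this review takes no position on it.

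The cost is about one sentence in an amendment, plus matching wording in the cross-referenced places. The test itself is already in the protocol. If entry is complete, a note to file recording which test was used as Day 0 for each woman of childbearing potential would give the pregnancy listings in section 9.9 a clear baseline source.

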### 7.3. Clinical Laboratory Tests

The following laboratory parameters will be assessed upon the subjects return to the clinical unit every 6 months:

Serum chemistry	
Sodium	Globulin
Potassium	Alkaline phosphatase
Chloride	AST
Bicarbonate	ALT
Blood urea nitrogen	Gamma glutamyl transferase
Creatinine	Cholesterol
Calcium	Uric acid
Inorganic Phosphorous	Thyroid-stimulating hormone
Glucose	Total thyroxine (T4)
Total bilirubin	Free T4
Total proteins	Prealbumin (transthyretin)
Albumin	Retinol-binding protein
NT-pro-BNP	Troponin I

Coagulation	
Prothrombin time	INR

Hematology	
Hemoglobin	Platelets
Hematocrit	White blood cell count
Red blood cell count	Neutrophils
Packed cell volume	Lymphocytes
Mean corpuscular volume	Monocytes
Mean corpuscular hemoglobin	Eosinophils
Mean corpuscular hemoglobin concentration	Basophils

Urinalysis	
pH	Blood (free Hb)
Protein	Nitrite
Glucose	Urobilinogen
Ketones	Specific gravity
Bilirubin	

A central laboratory will be used to assess the parameters above. A manual will be provided to the sites describing the sample collection, storage, and shipping process. Approximately 8 mLs of blood will be collected at every visit when the laboratory parameters listed above are assessed.

The staff at the clinical unit will be instructed to review the source documentation (ie, central laboratory reports). For any abnormal laboratory result, the Investigator will be instructed to determine whether the result is “clinically significant” or “not clinically significant” by entering “CS” or “NCS”, respectively, directly on to source documentation. If an abnormal laboratory result is assessed as CS, then a corresponding AE should be recorded in the CRF.

---

